8.12.2 Tipping Point Analysis

A tipping point analysis will be used to explore the sensitivity of the results to the missing at random assumption (MAR) used in the main multiple imputation model. A range of treatment effects in those missing outcome data will be considered by adding a shift parameter to the multiple imputation model described above. This shift parameter, δ , will be applied only to study participants in the treatment group, and thus create a systematic difference in the missing outcomes across arms beyond what is observed in the data. For each value of δ , multiple imputed data sets will be created and analyzed as above. The results of these analyses will allow us to calculate the change in the mean transthyretin in those missing the primary outcome that would alter the conclusion of the primary study results.

Last Observation Carried Forward

As a sensitivity analysis, we will analyze the data using the last observation carried forward for those subjects with missing primary outcome data.

9. Sample Size Calculations / Power

With 500 participants this study has 80% power to detect a difference of 2.4 mg/dl in average circulating transthyretin levels during the third week between the protein supplementation group (assumed average circulating transthyretin level of 14.4, and the standard of care group (assumed average circulating transthyretin level of 12.0, with a pooled standard deviation of 7.0). This conservatively assumes that there will be 25% of the patients for whom the protein supplementation has no effect in that they are either well enough to have high circulating transthyretin levels or die prior to obtaining the primary outcome. Because the primary outcome is a surrogate marker, we do not plan for any formal interim analyses to evaluate efficacy or futility. Safety of our intervention will be reviewed by an independent Data Safety Monitoring Board (DSMB) on a regular basis. Currently, the Harborview Medical Center typically admits about 300 - 350 trauma victims per year who would meet eligibility criteria. With enrollment over 4 - 5 years, we anticipate that ~1500 patients will be eligible. Therefore, the rate of recruitment among eligible patients needs to be ~33%. The statistical analysis of the primary hypothesis will use a two-sided t-test with alpha of 0.05. We expect that less than 10% of patients will die prior to day 21. For these and for patients who are lost-to-follow-up prior to day 21, we will multiply impute the primary outcome separately for each group and incorporate previously observed circulating transthyretin levels (if available) and patient age information as well as sex, race/ethnicity, NUTRIC score, and ventilator free days.

10. Statistical and Data Programming

All data cleaning and programming will be done in either the statistical software R (R Foundation) or in SAS (SAS).

References (for this document: Statistical Design and Power)

2. Rubin DB. *Multiple imputation for nonresponse in surveys*. Wiley series in probability and mathematical statistics Applied probability and statistics,. Wiley; 1987:xxix, 258 pages.

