1.6 Study procedures

Screening of all potential subjects will be done by the Registered Dietitian who is assigned to the Critical Care team and is a member of the research team. Potential study subjects will be identified upon admission to the critical care unit and considered for enrollment if they meet inclusion criteria. Once a subject has been identified, we will randomize that subject into one of the two treatment arms. We will randomly assign subjects to receive either additional enteral protein to achieve a total of 2g/kg/day of protein or to standard enteral nutritional support. Due to the limited published information and the variation across hospitals and within our own practice, both treatment groups can be considered standard care. At Harborview, there is no protocol utilizing one method of protein dosing vs the other. Both are approaches used in our critically ill surgical and trauma patients. The University of Washington Institutional Review Board has approved this study with a waiver of documented consent as it is considered minimal risk (.

We will use a **randomized design** to test whether supplementing enteral protein improves patient care and outcomes. Subjects will be followed until discharged from the hospital and clinical data will be obtained from the electronic medical record. The randomization will be done by previously sealed envelopes that contain an equal number of each treatment assignment. Subjects are randomized 1:1 to either no or additional enteral protein.

Standard of care at our institution includes obtaining nutrition-related labs. Vitamin C, Vitamin D, Zinc and other vitamins and micronutrients are typically measured within 24 hours of ICU admission and used to guide supplementation and treat any deficiencies. Circulating transthyretin (TTHY), C-reactive protein (C-RP) are measured approximately weekly in patients requiring greater than 7 – 10 days of nutritional support. Similarly, we often obtain urine for 24-hour total urinary nitrogen (TUN) measurements, and indirect calorimetry (this is a measure, not a lab procedure) after 7 – 10 days of support. Indirect calorimetry is used to adjust caloric intake and to better understand a patient's general use of energy sources. In this trial the dietitian and

clinical team may adjust caloric goals based upon indirect calorimetry. We will not adjust protein intake based upon TUN or TTHY measurements.

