Statistical Analysis Plan:

**Supplemental enteral protein in critically ill trauma and surgical patients: A
randomized clinical trial**

NCT03170401

August 20, 2023

1. Trial Synopsis

The aim of this study is to determine the effect of enteral protein supplementation on biochemical measures of inflammation and protein metabolism in critically ill surgical patients. The investigators will also collect data on important clinical outcomes, including infectious complications, duration of mechanical ventilation and other measures of recovery from critical illness.

Overall Hypothesis: That early supplemental enteral protein will increase serum concentrations of transthyretin at three weeks after the onset of illness or injury. Secondarily, we will test whether supplementation increases ventilator-free days and reduces ventilator-associated pneumonia.

2. Primary Objective

Overall Aim: To determine the effect of enteral protein supplementation on serum protein markers, ventilator-free days, and complications in critically ill trauma victims.

Primary Hypothesis: That early supplemental protein will increase serum concentrations of transthyretin at two weeks after injury.

Secondary hypothesis: that supplementation improves clinical outcomes shown by an increase in ventilator free days (reduced duration of mechanical ventilation).

3. Design

The trial will use an open label parallel randomized trial design with a planned 500 patients receiving enteral nutrition randomized 1:1 to 2 g/kg/day of protein vs standard care.

4. Primary Estimand Statement¹

Population: critically ill adult trauma patients who are started on enteral nutrition within 72 hours after injury and are expected to require nutritional support for at least 1 week. Non-trauma post-surgical patients meeting study entry criteria will be included as well. This is expected to include patients recovering from emergency surgery, including amputations, debridement of necrotizing soft-tissue infections, and other serious surgical illnesses.

Treatments: Enteral protein with a target rate of 2 g/kg/day vs standard enteral nutrition.

Variable of Interest: Circulating transthyretin at 3 weeks (14-21 days after injury)

Primary efficacy analysis population definition: All randomized participants

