Intercurrent events: Subjects may be missing transthyretin due to death, discharge from the hospital, or recovery. Those participants who die will have a transthyretin level equal to the lowest value observed amongst the surviving subjects. Participants who are discharged alive

from the hospital before the primary outcome is measured will have a transthyretin level set equal to the highest observed measure. Multiple imputation will be used to account for study participants who did not have transthyretin measured in the expected window.

Summary measure: The difference in mean transthyretin levels between treatment arms.

5. Study Population

The investigation will enroll 500 subjects using the following inclusion and exclusion criteria:

Inclusion: critically ill adult trauma patients who are started on enteral nutrition within 72 hours of admission to the intensive care unit and are expected to require nutritional support for at least 1 week. Non-trauma post-surgical patients meeting study entry criteria will be included as well. This is expected to include patients recovering from emergency surgery, including amputations, debridement of necrotizing soft-tissue infections, and other serious surgical illnesses.

Exclusion: An individual who meets *any* of the following criteria will be excluded from participation in this study:

- Significant chronic organ failure,
- severe malnutrition,
- not expected to survive due to severity of injuries and,
- serum creatinine >2 mg/dl.

6. Data sources

Data will be collected concurrently with study subject enrollment and treatment in the intensive care unit. extracted from the electronic medical record.

7. Outcomes

7.1 Primary endpoint:

Circulating transthyretin concentrations measured 14 – 21 days after injury.

7.2 Secondary endpoint:

- Ventilator free days: the numbers of days on which the subject does not require assisted ventilation during the first 28 days following the date of injury. VFD will be set to zero for all participants who die before hospital discharge.
- Hospital acquired pneumonia: Pneumonia diagnosed while the patient is in the hospital. Pneumonia will be defined as the presence of a positive quantitative culture from a bronchoalveolar lavage sample coupled with the use of antibiotics.

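### LOCF enters a pre-window transthyretin value as a week-3 value, so it cannot serve as a robustness check beside the tipping-point analysis

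*SAP*

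**What the plan says.** SAP 8.12.2 ends with a short paragraph on LOCF: as a sensitivity analysis, "we will analyze the data using the last observation carried forward" for participants whose primary outcome is missing. It gives no rationale, no guidance on reading the result, and no rule for a participant with no earlier value.

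Other parts of the plan bear on this:

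- **Endpoint.** SAP 7.1 and 8.5 set the window at days 14–21.
- **Sampling.** Protocol 1.6 says transthyretin is "measured approximately weekly in patients requiring greater than 7 – 10 days of nutritional support".
- **Time course.** SAP 8.9 compares the rate of increase between arms in a GEE model with an arm-by-day interaction.
- **Assigned scores.** SAP 4 gives deaths the lowest value seen in survivors. Participants who leave alive "from the hospital before the primary outcome is measured will have a transthyretin level set equal to the highest observed measure". Multiple imputation covers those not measured in the window.
- **Main sensitivity analysis.** SAP 8.12 and 8.12.2 specify a tipping-point analysis that shifts imputed values in the treated arm, aimed at the missing-at-random (MAR) assumption.

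**The concern.** LOCF assumes that a participant's transthyretin stays at its last recorded level until week 3. The plan itself expects the marker to rise, and allows the rise to differ by arm. With weekly sampling, the last value before an unmeasured window will often be about a week old or older.

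Two further features weaken the analysis. A carried value is entered as if observed, so the standard error makes no allowance for the gap between it and the unseen week-3 value; the primary analysis makes that allowance through Rubin's rules. The scope is also unclear. SAP 4 scores deaths and live discharges, while SAP 8.12, 8.12.1 and 9 treat deaths as missing and impute them. If LOCF covers scored participants, it replaces the highest score of an early live discharge with an earlier reading, and so answers a different question from the primary analysis.

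What is at stake is interpretation. Disagreement with the primary result might come from the method alone, and agreement might be accidental.

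**Working it through.** **1. The plan's own figure.** SAP 9 states: "With 500 participants this study has 80% power to detect a difference of 2.4 mg/dl in average circulating transthyretin levels", "with a pooled standard deviation of 7.0", tested by a "two-sided t-test with alpha of 0.05". Allocation is equal (SAP 3: "randomized 1:1 to 2 g/kg/day of protein vs standard care"), so 250 per arm. SAP 9 also assumes "there will be 25% of the patients for whom the protein supplementation has no effect".

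- Diluted difference: 0.75 × 2.4 = 1.8 mg/dl.
- Standard error: 7.0 × √(2/250) = 0.626.
- Power: Φ(1.8/0.626 − 1.96) = Φ(0.915) = 0.82, which matches the stated 80% closely.
- Without the dilution, power would be 0.97, so the diluted reading is the one that reproduces the figure.

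LOCF does not enter this calculation.

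**2. Equal missingness.** Let *m* be the share of values carried in each arm, and *f* the arm difference at the carried day as a fraction of the week-3 difference. The expected LOCF difference is

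2.4 × [(1 − m) + m × f].

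The documents give neither *m* nor *f*; both are assumed here. For a day-7 value, take a difference of zero at the start (expected under randomization) that grows linearly, in line with the arm-by-day term in SAP 8.9. The mid-window day is (14 + 21)/2 = 17.5, so f = 7/17.5 = 0.4.

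| Share carried (m) | f = 0 | f = 0.4 (day 7) | f = 1 | f = 1.25 |
|---|---|---|---|---|
| 10% | 2.16 | 2.26 | 2.40 | 2.46 |
| 25% | 1.80 | 2.04 | 2.40 | 2.55 |
| 40% | 1.44 | 1.82 | 2.40 | 2.64 |
| 50% | 1.20 | 1.68 | 2.40 | 2.70 |

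For example, at 25% and f = 0.4: 2.4 × (0.75 + 0.10) = 2.04, or 15% too small. At 40%: 2.4 × (0.60 + 0.16) = 1.82, or 24% too small. Starting from the diluted 1.8 gives the same percentages (1.8 × 0.85 = 1.53).

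**3. Unequal missingness.** Use the plan's week-3 means, 14.4 and 12.0 (SAP 9), with an assumed common early level of 8 mg/dl and no early arm difference.

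- 15% carried in the treated arm, 35% in control: (0.85 × 14.4 + 0.15 × 8) − (0.65 × 12.0 + 0.35 × 8) = 13.44 − 10.60 = 2.84.
- 35% treated, 15% control: (0.65 × 14.4 + 0.35 × 8) − (0.85 × 12.0 + 0.15 × 8) = 12.16 − 11.40 = 0.76.

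With an assumed early level of 10 mg/dl, the same two splits give 2.44 and 1.16. Which arm loses more values decides the direction, and the documents do not say.

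**The case against.** The strongest reply is that little depends on LOCF. It is one supplementary analysis with no conclusion tied to it, and the tipping-point analysis already tests departures from MAR. That stands, and it keeps the point small.

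A reader might infer that LOCF necessarily shrinks the effect. The documents do not support this: they give no missingness rate by arm and no early arm difference. The table shows no shrinkage at f = 1, and step 3 shows possible inflation. For the same reason LOCF cannot be defended as dependably conservative.

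A reader might also infer that LOCF drops participants with no earlier sample, against the inclusion of everyone randomized in SAP 8.4. The SAP is silent on this, so it is a gap in the rule and not a stated exclusion. Nor is it established that LOCF overrides the scores in SAP 4; if scored participants stay scored, fewer values are carried.

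The proposed mixed model has limits too. It relies on MAR, as the primary imputation does; it takes no outcome information from participants without any value; and with no assigned scores it implicitly models values after death. These objections stand and must be stated in its label. Its advantage over LOCF is that each value is used on the day it was taken.

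Finally, Protocol 3.4 places initial analyses before record reviews held in January to April 2023, and the SAP is dated August 2023. Quiet removal of a listed analysis could look selective. That also stands, and it shapes the fix.

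**Conclusion.** The concern holds in conditional form. LOCF in SAP 8.12.2 enters a pre-window value as a week-3 value for a marker that the plan models as rising at rates that may differ by arm. With similar missingness and an effect that grows over time, it shrinks the arm difference, for example from 2.4 to about 2.0 mg/dl with 25% carried from day 7. With unequal missingness the bias can go either way. The carried share, carried day, early level and early effect are all assumptions. An analysis whose bias has unknown size and direction, and which treats carried values as measured, cannot show robustness. The effect is confined to a supplementary analysis: N = 500, power of about 82% on the plan's inputs, and the primary test do not change.

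**What to change.** Make a dated SAP change, with its reason, noting that initial analyses had already been done:

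1. Replace LOCF as the sensitivity analysis with a mixed model that uses all available transthyretin values and estimates the arm difference over days 14–21.
2. Label that model as relying on MAR, and as estimating a different quantity from the primary estimand because it assigns no scores to deaths and live discharges.
3. Keep the tipping-point analysis as the test of MAR, and leave the GEE slope analysis in SAP 8.9 as it is.
4. If LOCF is still reported for transparency, label it supportive only, state its no-change assumption, say whether scored deaths and discharges count as missing, and say what happens when there is no earlier value.

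The cost is some SAP text, one extra model, and a result that is not directly comparable with the scored primary analysis. No new data are needed.
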